6.3.7 Hy's law

Cases where a subject shows an AST or ALT $\geq 3 \times \text{ULN}$ or total bilirubin $\geq 2 \times \text{ULN}$ may need to be reported as SAEs. Prompt reporting of cases meeting Hy's law criteria (via the SAE expedited reporting system) is required for compliance with regulatory guidelines. The investigator is responsible for, without delay, determining whether a patient meets potential Hy's law (PHL) criteria.

Details of identification of PHL cases and actions to take are detailed in [Appendix E](#).

6.3.8 Disease progression

Disease progression can be considered as a worsening of a subject's condition attributable to the disease for which the investigational product is being studied. It may be an increase in the severity of the disease under study and/or increases in the symptoms of the disease. The development of new, or progression of existing metastasis to the primary cancer under study should be considered as disease progression and not an AE. Events, which are unequivocally due to disease progression, should not be reported as an AE during the study.

6.3.9 New cancers

The development of a new cancer should be regarded as an AE and will generally meet at least one of the serious criteria. New cancers are those that are not the primary reason for the

administration of the study treatment and have been identified after the patient's inclusion in this study. They do not include metastases of the original cancer.

6.3.10 Handling of deaths

All deaths that occur during the study, or within the follow-up period after the administration of the last dose of investigational product, should be reported as follows:

- Death, which is unequivocally due to disease progression, should be communicated to the study monitor at the next monitoring visit and should be documented in the CRF module, but should not be reported as a SAE during the study
- Where death is not clearly due to disease progression of the disease under study the AE causing the death should be reported to the study monitor as an SAE within 24 hours. The report should contain a comment regarding the co-involvement of progression of disease, if appropriate, and should assign a single primary cause of death together with any contributory causes
- Deaths with an unknown cause should always be reported as a SAE but every effort should be made to establish a cause of death. A post-mortem may be helpful in the assessment of the cause of death, and if performed a copy of the post-mortem results (with translation of important parts into English) should be reported in an expedited fashion to an AstraZeneca representative within the usual timeframes

6.4 Reporting of serious adverse events

All SAEs have to be reported, whether or not considered causally related to the investigational product, or to the study procedure(s). All SAEs will be recorded in the CRF.

If any SAE occurs in the course of the study, then Investigators or other site personnel inform the appropriate AstraZeneca representatives within one day i.e., immediately but **no later than 24 hours** of when he or she becomes aware of it.

The designated AstraZeneca representative works with the Investigator to ensure that all the necessary information is provided to the AstraZeneca Patient Safety data entry site **within 1 calendar day** of initial receipt for fatal and life threatening events **and within 5 calendar days** of initial receipt for all other SAEs.

For fatal or life-threatening adverse events where important or relevant information is missing, active follow-up is undertaken immediately. Investigators or other site personnel inform AstraZeneca representatives of any follow-up information on a previously reported SAE within one calendar day i.e., immediately but **no later than 24 hours** of when he or she becomes aware of it.

Once the Investigators or other site personnel indicate an AE is serious in the WBDC system, an automated email alert is sent to the designated AstraZeneca representative.

If the WBDC system is not available, then the Investigator or other study site personnel reports a SAE to the appropriate AstraZeneca representative by telephone.

The AstraZeneca representative will advise the Investigator/study site personnel how to proceed.

The reference document for definition of expectedness is the IB for the AstraZeneca drug AZD9291 and the EU Summary of Product Characteristics (SPC) for the active comparator product (including any AstraZeneca comparator).

6.5 Overdose

Investigators are advised that any patient who receives a higher dose than intended should be monitored closely, managed with appropriate supportive care and followed up expectantly.

Such overdoses should be recorded as follows:

- An overdose with associated AEs/SAEs is recorded as the AE diagnosis/symptoms on the relevant AE/SAE modules in the CRF and on the Overdose CRF module.
- An overdose without associated symptoms is only reported on the Overdose CRF module.

If an overdose on an AstraZeneca study drug occurs in the course of the study, then the Investigator or other site personnel inform appropriate AstraZeneca representatives immediately, or **no later than 24 hours** of when he or she becomes aware of it.

The designated AstraZeneca representative works with the Investigator to ensure that all relevant information is provided to the AstraZeneca Patient Safety data entry site.

For overdoses associated with a SAE, the standard reporting timelines apply, see Section 6.4. For other overdoses, reporting must occur within 30 days.

6.6 Pregnancy

All pregnancies and outcomes of pregnancy should be reported to AstraZeneca during the course of the study and within 28 days of the last dose of AZD9291.

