3.5 Restrictions

The following restrictions apply while the patient is receiving study treatment and for the specified times before and after:

1. Females of child-bearing potential should use reliable methods of contraception from the time of screening until 3 months after discontinuing study treatment. Acceptable methods of contraception include abstinence, tubal ligation, oral or transdermal contraceptives, copper-banded intra-uterine devices and vasectomised partner. All hormonal methods of contraception should be used in combination with the use of a condom by their male sexual partner for intercourse.
2. Male patients should be asked to use barrier contraceptives (ie, by use of condoms) during sex with all partners during the trial and for a washout period of 3 months. Patients should avoid procreation for 6 months after completion of trial treatment. Patients should refrain from donating sperm from the start of dosing until 6 months after discontinuing study treatment. If male patients wish to father children they should be advised to arrange for freezing of sperm samples prior to the start of study treatment.
3. Once enrolled all patients must try to avoid concomitant use of medications, herbal supplements and/or ingestion of foods with known potent potent inhibitors of CYP2C8 and potent inhibitors or inducers of CYP3A4 whenever feasible, but patients may receive any medication that is clinically indicated for treatment of adverse events. Such drugs must have been discontinued for an appropriate period before they enter screening and for a period of 3 months after the last dose of AZD9291. All concomitant medications should be captured on the eCRF. Guidance on medicines to avoid, medications that require close monitoring and on washout periods is provided (see [Appendix F](#)).

4. If medically feasible, patients taking regular medication, with the exception of potent inhibitors or inducers of CYP3A4 and inhibitors of CYP2C8 (see above), should be maintained on it throughout the study period. Patients taking concomitant medications whose disposition is dependent upon CYP3A4 or CYP2C8 and which have a narrow therapeutic index should be closely monitored for signs of changed tolerability as a result of increased exposure of the concomitant medication whilst receiving AZD9291. Guidance on medications to avoid, medications that require close monitoring and on washout periods should be provided (see [Appendix F](#)).

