6.3 Recording of adverse events

6.3.1 Time period for collection of adverse events

Adverse Events will be collected from time of signature of informed consent throughout the treatment period and including the safety follow-up period. The follow-up period is defined as 28 days after study treatment is discontinued. SAEs occurring in the follow-up period should be reported to AstraZeneca in the usual manner (see Section [6.4](#)).

Following discontinuation of AZD9291, SAEs considered related to study procedures should continue to be collected as outlined in [Table 8](#).

After the final database lock, there may be some patients remaining on study treatment. For these patients who are continuing to receive AZD9291 AstraZeneca will collect information (during the treatment period and for 28 days after last dose) on SAEs, deaths (including those due to disease progression), discontinuation due to AEs/SAEs and drug accountability only.

Table 8 Summary of recording and follow-up of adverse events and deaths

	Consent to Treatment Period	Until 28-day Follow-up Visit (safety follow-up period)	Post 28-day Follow-up visit but prior to progression (if applicable)	Post 28-day Follow-up visit and post progression (survival follow-up period)
Collect all new AEs in CRF	Yes	Yes	No	No
Collect all ongoing AEs in CRF	Yes	Yes	Yes	Yes
Collect all study procedure-related SAEs in CRF	Yes	Yes	Yes	Yes
Death due to AE, or unknown cause¹	Yes	Yes	No	No

¹ for example, death not due to disease progression, refer to Section [6.3.10](#)

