6.6.1 Maternal exposure

If a subject becomes pregnant during the course of the study investigational product should be discontinued immediately.

Pregnancy itself is not regarded as an adverse event unless there is a suspicion that the investigational product under study may have interfered with the effectiveness of a contraceptive medication. Congenital abnormalities/birth defects and spontaneous miscarriages should be reported and handled as SAEs. Elective abortions without complications should not be handled as AEs. The outcome of all pregnancies (spontaneous

miscarriage, elective termination, ectopic pregnancy, normal birth or congenital abnormality) should be followed up and documented even if the subject was discontinued from the study.

If any pregnancy occurs in the course of the study or within 28 days of the final dose of the investigational product, then the Investigator or other site personnel informs the appropriate AstraZeneca representatives within 1 day i.e., immediately but **no later than 24 hours** of when he or she becomes aware of it.

The designated AstraZeneca representative works with the Investigator to ensure that all relevant information is provided to the AstraZeneca Patient Safety data entry site within 1 or 5 calendar days for SAEs (see Section 6.4) and within 30 days for all other pregnancies.

The same timelines apply when outcome information is available.

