6.6.2 Paternal exposure

Pregnancy of the subject's partners is not considered to be an adverse event. However, the outcome of all pregnancies (spontaneous miscarriage, elective termination, ectopic pregnancy, normal birth or congenital abnormality) should if possible be followed up and documented. To capture information about a pregnancy from the partner of a male subject, the male subject's partner consent must be obtained to collect information related to the pregnancy and outcome; the male subject should not be asked to provide this information. A consent form specific to this situation must be used. The outcome of any conception occurring from the date of the first dose until 6 months after dosing should be followed up and documented.

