exposure when coadministered with AZD9291. It is recommended that the starting and maintenance dose of statins should be as low as possible and should be guided by the statin label. Monitoring of low-density lipoprotein (LDL) cholesterol levels is advised. If the patient experiences any potentially relevant adverse events suggestive of muscle toxicity including unexplained muscle pain, tenderness, or weakness, particularly if accompanied by malaise or fever, the statin should be stopped, creatine kinase (CK) levels should be checked, and any appropriate further management should be taken. Patients taking warfarin should be monitored regularly for changes in prothrombin time or INR.

Revised text:

1. Females of child-bearing potential should use reliable methods of contraception from the time of screening until 3 months after discontinuing study treatment. Acceptable methods of contraception include **total sexual** abstinence, tubal ligation, hormonal contraceptives that are not prone to drug-drug interactions [IUS Levonorgestrel Intra Uterine System (Mirena), Medroxyprogesterone injections (Depo-Provera)], copper-banded intra-uterine devices and vasectomised partner. All hormonal methods of contraception should be used in combination with the use of a condom by their male sexual partner for intercourse.
2. Once enrolled all patients must try to avoid concomitant use of medications, herbal supplements and/or ingestion of foods with known ~~potent inhibitors of CYP2C8 and~~ potent inhibitors or inducers of CYP3A4 whenever feasible, but patients may receive any medication that is clinically indicated for treatment of adverse events. Such drugs must have been discontinued for an appropriate period before they enter screening and for a period of 3 months after the last dose of AZD9291. All concomitant medications should be captured on the eCRF. Guidance on medicines to avoid, medications that require close monitoring and on washout periods is provided (see Appendix F).

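### The pregnancy notification window in 6.6 and 6.6.1 does not match the 3-month contraception period in 3.5 or the 6-month partner window in 6.6.2, and no follow-up contact asks about pregnancy

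*Supplement*

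**What the plan says.** Four sections of the protocol set post-treatment windows that bear on pregnancy.

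- Section 6.6 gives the general rule: "All pregnancies and outcomes of pregnancy should be reported to AstraZeneca during the course of the study and within 28 days of the last dose".
- Section 6.6.1 (maternal exposure) sets the condition for notifying the sponsor within 24 hours of awareness: "If any pregnancy occurs in the course of the study or within 28 days of the final dose of the investigational product".
- Section 3.5, in the text revised by Amendment 2, reads: "Females of child-bearing potential should use reliable methods of contraception from the time of screening until 3 months after discontinuing study treatment". For men the same section says: "Patients should avoid procreation for 6 months after completion of trial treatment".
- Section 6.6.2 (paternal exposure) says: "The outcome of any conception occurring from the date of the first dose until 6 months after dosing should be followed up and documented".

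Both amendments revise the female contraception item in 3.5. Neither touches 6.6, 6.6.1 or 6.6.2.

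Section 6.3.1 sets the post-treatment safety period: "The follow-up period is defined as 28 days after study treatment is discontinued". Section 7.8 follows patients who stay on drug after the final cut-off for 28 days past their last dose, for new treatment-related serious adverse events.

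**The concern.** For men, the 6 months of follow-up in 6.6.2 equal the 6 months of avoided procreation in 3.5. For women, who are exposed directly, the only stated number of days for notification is 28, against 3 months of required contraception. The general rule in 6.6 covers every pregnancy, so its 28 days also sit awkwardly beside the 6 months for partners.

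Take a woman who conceives around day 40 after her last dose. She is still inside the contraception period. Whether her site must notify the pregnancy depends on how it reads the course of the study, a term that 6.6 does not define. Sites may read it differently.

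Pregnancies exposed to an investigational drug are rare, so each one that is not notified is a real loss of safety information. No efficacy endpoint or analysis set is affected.

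**Working it through.** The plan gives no figure to reproduce. The check compares windows and then applies each reading of the notification rule.

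**Inputs**
- Notification window after the last dose: 28 days (6.6, 6.6.1).
- Female contraception after stopping treatment: 3 months (3.5). Assumed to be 91 days.
- Partner conception follow-up: 6 months (6.6.2). Assumed to be 183 days.
- Survival contacts: every 6 weeks, that is 42 days, with a window of ±7 days (4.3.4, Table 1).

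**Narrow reading: the course of the study means treatment plus the 28-day safety follow-up**
- Days without an explicit maternal notification duty: 91 − 28 = 63.
- Share of the contraception period: 63 / 91 = 69%. Taking 3 months as 90 or 92 days gives 62 / 90 = 69% or 64 / 92 = 70%, so the convention hardly matters.

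There is some support for this reading. Section 6.3.1 defines safety follow-up as 28 days. For deaths, 6.3.10 uses a similar two-part phrase: "All deaths that occur during the study, or within the follow-up period after the administration of the last dose of investigational product". Table 8 then stops collecting deaths from an adverse event or unknown cause after the 28-day visit. This is only an analogy, because Table 8 has no pregnancy row.

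**Broad reading: the course of the study includes progression and survival follow-up**
- Section 9.3 ends the study at the last subject's last visit, and 3.7 treats withdrawal from the study as stopping both treatment and assessments. A woman off drug but still followed is therefore in the study, and a conception on day 40 is notifiable.
- Only the 28-day limb then applies to two groups: patients who have left the study, and patients treated after the final cut-off under 7.8. For them, days 29 to 91 have no explicit duty.
- Nothing puts the broad reading into practice. The items listed for progression follow-up (4.3.3) and survival follow-up (4.3.4) do not include pregnancy, and Table 1 has a pregnancy test at screening only.

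**Partner window**
- The 28 days in 6.6 are 28 / 183 = 15% of the period in 6.6.2, a difference of 183 − 28 = 155 days. This shows that 6.6 lacks a cross-reference. It does not measure lost cases, because 6.6.2 has its own rule.

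**Whether existing contacts could close the gap**
- Contacts 42 days apart, each allowed to move by 7 days, are at most 42 + 14 = 56 days apart. Since 56 < 63, at least one scheduled contact falls between day 29 and day 91 for any patient in 6-weekly follow-up.

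**The case against.** A reader might infer that maternal reporting stops at day 28 and that later exposures go unreported. The documents do not support that.

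- Section 6.6.1 joins its two limbs with *or*. For a patient still in follow-up, the plain wording reaches a pregnancy after day 28. **This stands**, and the 69% therefore holds only on the narrow reading.
- Section 6.6.1 also asks for the outcome of every pregnancy to be followed and documented, even after the subject has discontinued, with no 28-day limit. It would be wrong to say that a site has no duty to follow the outcome. **This stands**, although it helps only once the pregnancy is known.
- Section 6.6.1 treats birth defects and spontaneous miscarriages as serious adverse events, and 6.3.2 asks for any such event judged possibly related to be notified whenever the investigator learns of it. **This stands in part.** Pregnancy is generally not an adverse event in itself, so normal births, uncomplicated elective terminations and the count of exposed pregnancies are not caught this way.
- The 28-day limb is not empty on the broad reading. It reaches patients who have left the study and, on its wording, those under 7.8. **This stands**: their coverage is short, not absent.
- Section 6.6.2 is a specific rule for partners and can be read alongside the general rule in 6.6. **This stands**, and a cross-reference is enough there.
- Section 3.5 requires contraception; it does not declare a period of fetal risk, and no passage says that the reporting and contraception periods must be equal. **This is fair.** The case rests on the mismatch between the windows and on the missing collection procedure.

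**Conclusion.** The point holds as an inconsistency with an operational gap. On the narrow reading, about 63 of 91 post-treatment contraception days (69%) have no explicit duty to notify a maternal pregnancy. On the broad reading, the gap is confined to patients who have left the study or are treated after the final cut-off. The documents do not allow that number to be estimated. On either reading, no follow-up contact is set up to find a pregnancy.

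The figures assume that 3 months is about 91 days and that the date of the last dose and the date of discontinuation coincide. For women the comparator is the 3 months in 3.5; the 6 months concern partners of male patients only.

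The primary analysis is not affected. The point is still worth acting on because it concerns safety capture and is cheap to mend.

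**What to change.** Reconcile 6.6 and 6.6.1 with 3.5:

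1. State that maternal pregnancy notification runs at least to the end of the contraception period given in 3.5, whatever the patient's follow-up status, and including patients treated under 7.8.
2. In 6.6, refer to 6.6.2 for the separate partner window.
3. Add a pregnancy question, for women of child-bearing potential, at the existing follow-up contacts that fall within that period.

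The cost is a few sentences in an amendment, one question at contacts that already take place, and a small change to data capture. Survival information may come from family or another physician (4.3.4), so the question should be put to the patient where possible. Patients who have left the study, and those under 7.8 after their 28-day follow-up, have no such contacts. For them the explicit duty would apply when the site learns of a pregnancy. No change to the contraception rule is proposed.

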6.6.1 Maternal exposure

If a subject becomes pregnant during the course of the study investigational product should be discontinued immediately.

Pregnancy itself is not regarded as an adverse event unless there is a suspicion that the investigational product under study may have interfered with the effectiveness of a contraceptive medication. Congenital abnormalities/birth defects and spontaneous miscarriages should be reported and handled as SAEs. Elective abortions without complications should not be handled as AEs. The outcome of all pregnancies (spontaneous

miscarriage, elective termination, ectopic pregnancy, normal birth or congenital abnormality) should be followed up and documented even if the subject was discontinued from the study.

If any pregnancy occurs in the course of the study or within 28 days of the final dose of the investigational product, then the Investigator or other site personnel informs the appropriate AstraZeneca representatives within 1 day i.e., immediately but **no later than 24 hours** of when he or she becomes aware of it.

The designated AstraZeneca representative works with the Investigator to ensure that all relevant information is provided to the AstraZeneca Patient Safety data entry site within 1 or 5 calendar days for SAEs (see Section 6.4) and within 30 days for all other pregnancies.

The same timelines apply when outcome information is available.

6.6.2 Paternal exposure

Pregnancy of the subject's partners is not considered to be an adverse event. However, the outcome of all pregnancies (spontaneous miscarriage, elective termination, ectopic pregnancy, normal birth or congenital abnormality) should if possible be followed up and documented. To capture information about a pregnancy from the partner of a male subject, the male subject's partner consent must be obtained to collect information related to the pregnancy and outcome; the male subject should not be asked to provide this information. A consent form specific to this situation must be used. The outcome of any conception occurring from the date of the first dose until 6 months after dosing should be followed up and documented.

